9. Subject has a mean QTcF interval of > 430 msec (for males) and > 450 msec (for females) at Screening or check-in. If the mean QTcF exceeds the limits above, 1 additional triplicate ECG can be taken. If this triplicate also gives an abnormal result, the subject should be excluded.
10. Subject has a history of unexplained syncope, cardiac arrest, unexplained cardiac arrhythmias or *torsade de pointes*, structural heart disease, or a family history of Long QT Syndrome.
11. Subject has use of any prescribed or non-prescribed drugs (including vitamins, hormone replacement therapy, natural and herbal remedies, e.g., St. John's Wort) in the 2 weeks before study drug administration. Acetaminophen up to 2000 mg/day is allowed.
12. Subject has had any use of tobacco- or nicotine-containing products within 6 months prior to Screening.
13. Subject has history of consuming more than 14 units of alcoholic beverages per week within 6 months prior to Screening or has a history of alcoholism or abuse of amphetamines, barbiturates, benzodiazepines, cannabinoids, cocaine, and opiates (drugs-of-abuse) within the past 2 years prior to Screening (Note: 1 unit = 355 mL of beer, 118 mL of wine, or 29 mL of spirits/hard liquor) or the subject tests positive at Screening or site admission for alcohol or drugs-of-abuse.
14. Subject has used any drugs-of-abuse within 3 months before check-in.
15. Subject has used any inducers of metabolism (e.g., barbiturates, rifampin) in the 3 months prior to check-in.
16. Subject has any significant blood loss, donated 1 unit (450 mL) of blood or more, or received a transfusion of any blood or blood products within 60 days, or donated plasma within 7 days before check-in.
17. Subject has a positive serology test for hepatitis B surface antigen (HbsAg), anti-hepatitis A virus Immunoglobulin M (HAV IgM), anti-hepatitis C virus (HCV Ab), or anti-human immunodeficiency virus (HIV Ab).
18. Subject has participated in any interventional clinical study or has been treated with any investigational drugs within 3 months or 5 half-lives, whichever is longer, before the initiation of Screening.
19. Subject has (recent history of) any other condition which, in the opinion of the Investigator, precludes the subject's participation in the trial.
20. Subject is an employee of the Kainos Medicine, Inc. or vendors involved in the study.

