#### Exclusion Criteria for Elderly Subjects

##### Replacement for Exclusion No. 8 above

8. Subject has a mean pulse < 50 or > 90 bpm; mean SBP > 160 mmHg; mean DBP > 100 mmHg (measurements taken in triplicate after subject has been resting in supine position for 5 minutes; pulse will be measured automatically).

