#### 4.3 Subject Withdrawal and Replacement

A subject may withdraw from the study at any time without penalty and for any reason without prejudice to his/her future medical care. Participation of subjects may also be discontinued based on the medical judgment of the PI in conjunction with the Sponsor for any of the following reasons:

- ECG abnormalities:  
Any increases in QTcF > 500 msec or increase > 60 msec from baseline as confirmed with 3 consecutive ECGs taken within 5 minutes, with at least a 1-minute interval.
- Suicidality:  
Any suicide attempt or any recent suicidal ideation (a level of 4 or 5) since the last assessment, or a significant risk to commit suicide, as judged by the PI using the C-SSRS.
- Liver Safety Monitoring:  
Please refer to Stopping Criteria No. [2](#).
- After enrolment, the subject is found to violate the inclusion and/or exclusion criteria
- AE(s)
- Subject lost to follow-up
- Major protocol violation
- Use of prohibited medications mentioned in Section [5.8](#)
- The Investigator may, after discussion with the subject, withdraw the subject due to any serious safety concerns
- The study is terminated prematurely
- Other

In all cases, the reason(s) for withdrawal, and the primary reason, must be recorded on the electronic case report form (eCRF). Subjects who are withdrawn will have an Early Discontinuation (ED) Visit per the Schedules of Assessments (see Table [7-1](#) and Table [7-2](#)).

A subject may also be withdrawn from study by the Sponsor, Regulatory Authorities, or IECs/IRBs.

Subjects will also be withdrawn if the entire study is terminated prematurely as described in Section [9.10](#).

Withdrawn subjects may be replaced at the discretion of the Sponsor with agreement of the Investigator. Subjects who are discontinued because of treatment-emergent AE (TEAE) or possible toxic effects of the drug will not be replaced.

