#### 6.4.4 Electrocardiograms

Standard 12-lead ECGs will be performed in accordance with the Schedule of Procedures (Table 7-1 and Table 7-2).

ECG will be performed using an internationally recognized 12-lead cardiograph (10 sec. rhythm strip) after the subject has been resting in a supine position for 5 minutes. All records will be done in triplicate within 5 minutes, with at least a 1-minute interval. ECG printouts will include: date, time, at least 2-3 complexes for 12 leads data, HR, QRS duration, P-R interval, R-R interval, QT interval, and QTcF (QT interval corrected for HR according to Fridericia).

- $QTcF = QT \times R-R^{1/3}$

ECG recording will be performed according to the relevant site SOP. The review of the ECG must be done by the Investigator or delegate. The interpretation of the ECG result must follow the categories: “normal”, “abnormal, not clinically significant”, or “abnormal, clinically significant”. Clinically significant findings must be recorded as AEs, or if present at Screening, it should be documented as concomitant illness (see Section 6.4.1).

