The Statistical Analysis Plan (SAP) details the statistical methodology to be used in analyzing study data and outlines the statistical programming specifications for the Tables, Listings and Figures (TLFs). It describes the variables and populations, anticipated data transformations and manipulations and other details of the analyses not provided in the Clinical Study Protocol (CSP).

The analyses described are based on the final CSP 5.0, dated, 13/Feb/2017. The SAP will be finalized prior to database lock and describes the statistical analysis as it is foreseen when the study is being planned. If circumstances should arise during the study rendering this analysis inappropriate, or if improved methods of analysis should arise, updates to the analyses may be made. Any deviations from the SAP after database lock, reasons for such deviations and all alternative or additional statistical analyses that may be performed, will be described in a SAP Addendum.

PAREXEL International
Statistical Analysis Plan

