- **Liver enzymes:** alkaline phosphatase (ALP), aspartate aminotransferase (AST), alanine aminotransferase (ALT), and gamma-glutamyl transpeptidase (GGT).

Clinical significance of out-of-range laboratory findings is to be determined and documented by the Investigator/sub-Investigator who is a qualified physician. Clinically relevant changes will be recorded as AEs in the eCRF (see Section 6.4.1.2 of CSP).

For safety laboratory tests, the total volume of blood drawn will be approximately 51 mL for subject in Part A SAD, and approximately 51 mL for subject in Part B MAD. Additional safety samples may be collected if clinically indicated at the discretion of the investigator.

6.1.2.3 *Vital Signs*

The following vital signs measurements will be obtained at the time points mentioned in the table of assessments in the CSP section 7 (Table 7-1 and Table 7-3).

- Blood Pressure (BP), supine (systolic and diastolic; mmHg)
- Pulse, supine (beats per minute)
- Body temperature (°C) (tympanic)

BP and pulse will be measured using the normal practice at study center; after the subject has been in a supine position for at least 5 minutes.

6.1.2.4 *Electrocardiograms*

The following electrocardiogram (ECG) parameters will be recorded at the time points mentioned in the table of assessments in the CSP section 7 (Table 7-1 to Table 7-3).

ECG will be performed using an internationally recognized 12-lead cardiograph (10 sec. rhythm strip) after the subject has been resting in a supine position for 5 minutes. All records will be done in

PAREXEL International

Statistical Analysis Plan

triplicate within 5 minutes, with at least a 1-minute interval. ECG printouts will include: date, time, at least 2-3 complexes for 12 leads data,

- Heart rate (HR) (beats per minute [bpm])
- QRS-duration (msec)
- PR (PQ)-interval (msec)
- RR-interval (msec)
- QT-interval (msec)
- QTcF (QT interval corrected for HR according to Fridericia) (msec)

Where QTcF is calculated using $QTcF = QT \times R-R^{1/3}$

The review of the ECG must be done by the Investigator or delegate. The interpretation of the ECG result must follow the categories: “normal”, “abnormal, not clinically significant”, or “abnormal, clinically significant”. Clinically significant findings must be recorded as AEs, or if present at Screening, it should be documented as concomitant illness (see Section 6.4.1 of CSP).

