6.3.15.4 Twelve-Lead Electrocardiogram

All ECG parameters obtained from the ECG measurement will be listed [Listing 16.2.9.2.1 (Part A) and Listing 16.2.9.2.2 (Part B)] by subject for each study part by subject and time point including changes from baseline and repeat/unscheduled measurements. The mean of any triplicate assessments performed at a given time point will be used in all calculations of changes from baseline and in all tabulations. The baseline for each measurement will be the mean of the triplicate assessments obtained on Day -1.

PAREXEL International
Statistical Analysis Plan

All ECG parameters will be summarized [Table 14.3.6.2.1 (Part A) and Table 14.3.6.2.2 (Part B)], descriptive statistics (n, mean, SD, median, minimum, maximum) will be presented within each study part, and by cohort and time point for both observed values and changes from baseline.

No change from baseline will be calculated for screening visits.

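### QTcF is named as Fridericia but printed as QT multiplied by the cube root of RR, and the SAP lists RR in msec with no conversion to seconds

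*SAP*

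**What the plan says.** Protocol 6.4.4 lists what the ECG printout will contain: "HR, QRS duration, P-R interval, R-R interval, QT interval, and QTcF (QT interval corrected for HR according to Fridericia". One bullet follows, giving QTcF = QT × R-R^(1/3). The protocol states no unit for RR.

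SAP 6.1.2.4 repeats this list with units. It gives "RR-interval (msec" for RR, and msec for QT and QTcF as well. It then adds "Where QTcF is calculated using" followed by the same expression. Neither document contains another QTcF formula or a conversion of RR to seconds.

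On how the values are used, SAP 6.3.15.4 says "All ECG parameters obtained from the ECG measurement will be listed". It plans descriptive statistics for observed values and changes from baseline, with baseline taken as the Day -1 triplicate mean. The SAP's opening section says that the document "outlines the statistical programming specifications for the Tables, Listings and Figures (TLFs".

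**The concern.** The name and the formula do not agree. Fridericia's correction is QT / RR^(1/3), with RR in seconds. QT lengthens as RR lengthens, and dividing by RR^(1/3) removes that dependence. Multiplying by RR^(1/3) adds to it. The unit is a second problem: RR in msec put directly into either form gives a number on the wrong scale.

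The 12-lead ECG is a safety endpoint (protocol 3.2.1). Safety in young adults is the primary objective, and safety in the elderly is a secondary one. If a programmer derived QTcF from the SAP line as it stands, any change in heart rate would appear in the tables as a QTcF change. The QTcF summaries and changes from baseline in SAP 6.3.15.4 would then be wrong.

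**Working it through.** The documents give no worked QTcF value, so there is no figure to reproduce. The check compares the printed formula with the correction it names.

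**Inputs from the documents.** Entry pulse limits are 40 to 90 bpm for young adults (protocol 4.2, exclusion 8). For elderly subjects they are 50 to 90 bpm ("Subject has a mean pulse < 50 or > 90 bpm"). The expected scale of QTcF is set by the entry limits ("Subject has a mean QTcF interval of > 430 msec (for males) and > 450 msec (for females") and the individual discontinuation limits ("Any increases in QTcF > 500 msec or increase > 60 msec from baseline").

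**Assumed inputs.** True QTcF is 400 msec (range 380 to 430), and mean heart rate falls from 70 to 60 bpm. These are illustrations. The ratios in step 1 do not depend on the assumed QTcF.

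**Step 1: RR in seconds.** RR = 60/HR. If the true value is QTcF = QT / RR^(1/3), then QT = QTcF × RR^(1/3). The printed formula returns QT × RR^(1/3) = QTcF × RR^(2/3). Hence printed/correct = RR^(2/3), and uncorrected QT/correct = RR^(1/3).

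| HR (bpm) | RR (s) | printed/correct | uncorrected QT/correct |
|---|---|---|---|
| 40 | 1.500 | 1.310 | 1.145 |
| 50 | 1.200 | 1.129 | 1.063 |
| 60 | 1.000 | 1.000 | 1.000 |
| 70 | 0.857 | 0.902 | 0.950 |
| 90 | 0.667 | 0.763 | 0.874 |

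The printed formula is right only at 60 bpm. At every other rate it is further from the true value than QT with no correction.

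**Step 2: change from baseline, 70 to 60 bpm, true QTcF constant.**
- Base 400 msec, printed formula: 400 − 400 × 0.9023 = 400 − 360.9 = +39.1 msec.
- Base 400 msec, uncorrected QT: 400 − 400 × 0.950 = 400 − 380.0 = +20.0 msec.
- Base 380 msec, printed formula: +37.1 msec. Base 430 msec: +42.0 msec.

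**Step 3: RR in msec, printed formula.** Since 1000^(1/3) = 10, the result is 10 × 400 × RR^(2/3) with RR in seconds. This gives 5241 msec at 40 bpm, 4000 at 60 and 3053 at 90. None of these fits limits of 430, 450 or 500 msec.

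**Step 4: division restored, RR still in msec.** The result is 400/10 = 40 msec at every heart rate. The unit problem therefore remains even if the sign of the exponent is only a reading error.

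**The case against.** There are four arguments on the other side.

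1. **A minus sign may have been lost.** A multiplication sign is natural in the form QT × RR^(−1/3), so one lost superscript minus would explain the printed line. A similar loss may be visible in SAP 6.3.12, where the text on mean plots has a plus sign and slash before SD but no minus, while the matching figure titles in Section 9 have it. Agreement between protocol and SAP is weak confirmation, because the SAP section follows the protocol closely. This stands as a possibility, but neither document shows it. It also leaves the SAP's unit gap in place.

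2. **The cardiograph probably supplies QTcF.** It is a printout item in both documents, SAP 6.3.15.4 speaks of parameters obtained from the measurement, and the site needs the value for eligibility and for confirming an abnormal ECG. The SAP gives code for its pharmacokinetic models but none for QTcF. This largely stands: the documents lean this way, and the tables would then be unaffected. It does not settle the matter, because the SAP says QTcF is calculated by this formula and presents itself as a programming specification.

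3. **The unit is a reporting unit, and an error would be seen.** The msec label belongs to a listed parameter, and naming Fridericia implies seconds. Values near 40 or above 3000 would be noticed at once. That is fair, and it makes the msec readings unlikely to reach a report. It does not cover the case of RR in seconds, where a false 39 msec looks plausible.

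4. **The consequence is limited.** No QTcF test or categorical table is planned, and nothing ties a SAP-derived value to the protocol's QTcF limits. Nothing predicts a heart-rate change (protocol 1.2.1.2 reports none in dogs). A fall common to both arms would also appear in the pooled placebo group. The 1.31 to 0.76 range compares subjects at opposite pulse limits and is not a within-subject change. All of this stands and keeps the point minor.

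**Conclusion.** The formula is wrong as written in both documents, and the SAP also lacks the conversion of RR from msec to seconds. The point is minor.

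The effect on results is conditional. If the cardiograph's QTcF is summarised, there is none. If QTcF is derived as printed with RR in seconds, values are multiplied by RR^(2/3). That is 1.31 to 0.76 across the young-adult entry pulse range and 1.13 to 0.76 across the elderly range. For the assumed 10 bpm fall in mean heart rate, the false change from baseline is about 37 to 42 msec. If RR is entered in msec, the output is plainly impossible.

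Confidence is medium. The text reads the same way in both documents, but the exponent's sign has to be checked against the source PDFs, and the origin of the tabulated QTcF is not stated outright.

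**What to change.** - Check the formula line in both source PDFs for a minus sign in the exponent.
- In protocol 6.4.4 and SAP 6.1.2.4, print QTcF = QT / RR^(1/3), with QT in msec and RR in seconds (RR in msec divided by 1000).
- In SAP 6.3.15.4, add one sentence saying either that the cardiograph QTcF is listed and summarised, or that QTcF is derived with the corrected formula. A device-versus-derived comparison is optional.

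The cost is one line in each document and one sentence in the SAP. No new data are needed and no clinical limit changes.

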6.1.2.5 Physical Examination

The following physical examination parameters will be recorded at the time points mentioned in the table of assessments in the CSP section 7.

The examinations will include:

- General appearance
- Head, ears, eyes, nose, throat, neck
- Lymph node palpation
- Abdomen
- Skin
- Extremities
- Respiratory system
- Cardiovascular system
- Gastrointestinal system

Kainos Medicine, Inc.

KMCP-819-K101

Final 1.0

14/Nov/2017

TP-EP.BS-WW-001-05

Effective date: 29 Jul 15

Related to: SOP-EP.BS-WW-002

Page 21 of 61

PAREXEL International

Statistical Analysis Plan

- Musculoskeletal system
- Central and peripheral nervous system

If the subject experiences any changes during the visits which fulfill the criteria of an AE it must be recorded as such (see Section 6.4.1 of CSP).

6.1.2.6 Concomitant Medication

Concomitant medication will be coded using the World Health Organization-Drug Dictionary (WHO-DD) (Version WHO-DD **March 2016**) and will be classified by Anatomical Therapeutic Chemical (ATC) categories.

Any medication that the subject takes other than the study drug, including herbal and other non-traditional remedies, is considered a concomitant medication. Prior concomitant medications are defined as those taken from Screening until the time of the first study drug administration. Concomitant medications are defined as those taken at the time of or after the first study drug administration.

Concomitant medication will be coded using the World Health Organization-Drug Dictionary (WHO-DD) (Version WHO-DD **March 2016**) and will be classified by Anatomical Therapeutic Chemical (ATC) categories.

6.1.3 Pharmacokinetic Variables

Unless otherwise stated, derivation of pharmacokinetic (PK) parameters will be the responsibility of Quantitative Clinical Development (QCD), PAREXEL International. The following PK parameters will be determined for KM-819 in plasma following single dose administration:

PAREXEL International
Statistical Analysis Plan

Table 1 Pharmacokinetic Parameters after Single Dose Administration (Part A)

Parameter	Definition
C_{max}	Maximum plasma concentration determined directly from the concentration-time profile
t_{max}	Time to achieve maximum observed plasma concentration determined directly from the concentration-time profile
$t_{1/2}$	Apparent terminal elimination half life
Tlag	Lag time
λ_z	Terminal elimination rate constant
AUClast	Area under the plasma concentration-time from predose (time 0) to the last quantifiable concentration
AUC _{inf}	Area under the plasma concentration-time curve from predose (time 0) extrapolated to infinity
AUC(0-24)	Area under the plasma concentration-time from predose (time 0) to 24hrs postdose
%AUCex	Percentage of AUC _{inf} that is due to extrapolation beyond tlast
CL/F*	Apparent oral clearance
V_z/F^*	Apparent volume of distribution
AUCINF_D_obs	AUC _{inf} divided by dose
AUClast_D	AUClast divided by dose
Cmax_D	Maximum observed concentration divided by dose

*Parent drug only

This Table is applicable for Single ascending dose (Part A) and Day1 of Multiple ascending dose (Part B).

PAREXEL International
Statistical Analysis Plan

Table 2 Pharmacokinetic Parameters after Multiple Dose Administration

Parameter	Definition
C_{trough}	Observed concentration before dosing
C_{maxs}	Maximum plasma concentration determined directly from the concentration-time profile
C_{min}	Minimum plasma concentration determined directly from the concentration-time profile
t_{max}	Time to achieve maximum observed plasma concentration determined directly from the concentration-time profile
T_{lag}	Lag time
AUC_{tau}	Area under the plasma concentration-time curve for a dosing interval
AUC_{last}	Area under the plasma concentration-time from predose (time 0) to the last quantifiable concentration
CL/F^*	Apparent oral clearance
V_z/F^*	Apparent volume of distribution
$C_{av,ss}$	Average concentration at steady-state
$R_{ac}(AUC)$	Observed accumulation by AUC
$R_{ac}(C_{max})$	Observed accumulation by C_{max}
AUC_{tau_D}	AUC_{tau} divided by dose,
AUC_{last_D}	AUC_{last} divided by dose
C_{max_D}	Maximum observed concentration divided by dose

*Parent drug only

This Table is applicable for Day7 of Multiple ascending dose (Part B).

All urine voided will be collected in the following intervals: pre-dose and 0-24 hours post-dose. Urine samples will be used for qualitative analysis of KM-819 and possible metabolic profiling, if appropriate, and will be reported separately. For cerebrospinal fluid (CSF) PK, the concentration of KM-819 will be listed and no other PK parameters will be calculated as there will be only one sample from each subject.

PAREXEL International
Statistical Analysis Plan

6.1.3.1 *Pharmacokinetic Parameter Calculation Methods*

PK parameters will be calculated by non-compartmental analysis methods from the concentration-time data using WinNonlin (WNL) Professional (Version 6.3 or higher) following these guidelines:

- Actual sampling times relative to dosing rather than nominal times will be used in the calculation of all derived PK parameters.
- There will be no imputation of missing data.
- Any subjects with more than one observed concentration data will be included in the PK analysis set provided that at least C_{max} and $AUC_{(0-t)}$ can be reliably calculated .
- If one or more non-quantifiable (NQ) values occur in a profile before the first measurable concentration, they will be assigned a value of zero concentration. If a single NQ value occurs between measurable concentrations in a profile, the NQ should generally be omitted (set to missing) in the derivation of pharmacokinetic parameters, statistical analysis, and the individual subject plots. If two or more NQ values occur in succession between measurable concentrations, the profile will be deemed to have terminated at the last measurable concentration prior to these NQs. For the purpose of individual subject plots, these NQs will be set to 0, and the subsequent measurable concentrations will be retained. For the derivation of pharmacokinetic parameters, these NQs and any subsequent measurable concentrations will be omitted (set to missing).
- PK parameters following single and repeat dose will be estimated according to the following guidelines:
 - C_{max} will be obtained directly from the concentration-time data.
 - t_{max} is the time at which C_{max} is observed.
 - λ_z will be estimated at terminal phase by linear regression after log-transformation of the concentrations:
 - Only those data points that are judged to describe the terminal log-linear decline will be used in the regression.

PAREXEL International
Statistical Analysis Plan

- A minimum number of three data points in the terminal phase will be used in calculating λ_z with the line of regression starting at any post- C_{max} data point (C_{max} should not be part of the regression slope) and including C_{last} .
- The duration of time over which λ_z is estimated should generally be at least twice the subsequently estimated terminal phase half-life ($t_{1/2}$); exceptions to this duration made at the discretions of the PK scientist
- The adjusted correlation coefficient (R^2 adjusted) in general should be greater than 0.90. Any value less than 0.90 may be used at the PK Scientist's best knowledge and judgment.
- An appropriate number of decimal places should be used for λ_z to enable the reported value of $t_{1/2}$ to be calculated.
- $t_{1/2}$ will be calculated as $\ln 2 / \lambda_z$.
- AUC is calculated as follows:
 - The linear trapezoidal method will be employed for all incremental trapezoids arising from increasing concentrations and the logarithmic trapezoidal method will be used for those arising from decreasing concentrations.
 - $AUC_{(0-t)} = \int_0^t C(t) dt$. (AUCtau for repeat dose)
 - $AUC_{(0-\infty)} = \int_0^t C(t) dt + \int_t^{\infty} C(t) dt = AUC_{(0-t)} + C_t / \lambda_z$. (single dose only)
 - C_t is last observed quantifiable concentration.
- %AUC_{ex} will be calculated as $(1 - [AUC_{(0-t)} / AUC_{(0-\infty)}]) \times 100$.
- CL/F will be calculated as dose/AUC_(0-\infty), parent drug only.
- V_z/F will be calculated as CL/F/ λ_z , parent drug only.

The following PK parameters will also be derived using SAS

(version 9.2) or WinNonlin (WNL) Professional (Version 6.3 or higher) as deemed appropriate.

- R_{ac} Accumulation ratio calculated as:
 C_{max} (last dose interval)/ C_{max} (first dose interval).
 $AUC_{(0-t)}$ (last dose interval)/ $AUC_{(0-t)}$ (first dose interval).

PAREXEL International
Statistical Analysis Plan

